- 3) Objective responses were observed at SD-101 dose range of 1.0 mg – 8.0 mg in anti-PD-1/L1 inhibitor naïve patients, with tumor shrinkage at the injected and non-injected lesions.
- 4) A single patient responded and durable stable disease was seen at the 8.0 mg dose in anti-PD-1/L1 inhibitor experienced patients.
- 5) There were no DLTs.
- 6) SD-101 administered intratumorally in combination with IV pembrolizumab demonstrated no worsening of the expected toxicities of each of the individual monotherapies. The most common ($\geq 20\%$) treatment-related AEs were transient low-grade fatigue, myalgia, headache, chills and injection site reactions. Grade ≥ 3 treatment-related AEs were observed in 59.1% patients (most common: myalgia 13.6% and injection site pain 13.6%). Immune-related AEs occurred in 2 patients (2/22 or 9%).

One had a Grade 2 pneumonitis on Day 23 resulting in drug withdrawal and the other had hypophysitis (85 days after last treatment).

Based on preliminary review of the data, the efficacy of 2.0 mg per lesion was higher than 8.0 mg in one lesion in patients who are naïve to anti-PD-1/L1 and the RP2D was updated to 2.0 mg in 1 to 4 lesions and/or regions. The study with the new dosing of 2 mg per injection is ongoing also in patients who are resistant/refractory to anti-PD1/PD-L1 therapy.

A summary of the clinical studies conducted to date with SD-101 is provided in the Investigator's Brochure.

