7.6 Dose Modification, Dose Delays, and Missed Doses

NOTE: As of Amendment 9, irRECIST for the determination of disease progression is no longer applicable and this section has been revised accordingly.

Only a limited number of patients have been treated with SD-101, and to date, the most common toxicities include transient Grade 1 to 2 flu-like symptoms. In mice, SD-101 has been injected intratumorally concurrently with a neutralizing anti-mouse PD-1 antibody. In multiple experiments using high doses of SD-101 (approximately 2 mg/kg), no evidence of acute morbidity or mortality in mice was observed that could be due to the interaction of the 2 agents.

To protect patient safety, patients will be closely monitored for any additional or synergistic toxicities observed with the combination.

Withhold SD-101 for any Grade ≥ 3 injection-site reaction or drug-related AE that is not a DLT (see Section 9.1). SD-101 treatment may be resumed once the AE has resolved to Grade 0 or 1 with standard treatment. SD-101 must also be held for an ANC count of < 1500 cells/mcL.

Patients will be treated at the dose in their assigned Cohort and individual dose adjustment (reduction or increase) of SD-101 or pembrolizumab will not be permitted.

Delayed dosing of SD-101 would be preferred over completely skipping a dose as long as the interval between SD-101 dosing is not less than 5 days with subsequent return of SD-101 dosing to per protocol schedule of events. If the 5-day interval cannot be adhered to, then the injection must be skipped to allow a minimum of 5-day interval window between the off-scheduled injection and next injection on schedule. After a delayed or skipped dose, dosing will return to the original interval as described under Schedule of Trial Events.

For Phase 1, if ≥ 2 doses are missed during the DLT assessment period for any reason or if ≥ 4 doses are missed due to AEs following the DLT period, then SD-101 should be permanently discontinued. For Phase 2, if ≥ 4 doses are missed due to AEs, then SD-101 should be permanently discontinued.

If SD-101 dosing is delayed for more than 3 days, then the hematology and chemistry laboratory collections listed in the Schedule of Trial Events ([Appendix 1](#) through [Appendix 4](#)) or the planned day of dosing that were missed should be done prior to dosing on that day (eg, if Day 22 dosing is delayed and SD-101 is dosed on Day 26, then all the Day 22 labs should be repeated pre-dose on Day 26).

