SD-101 should be withheld if a patient requires greater than 10 mg per day of prednisone or equivalent to treat an AE (Section 9.3.2). SD-101 may be resumed when the corticosteroid is discontinued and pembrolizumab is resumed.

If an HNSCC subject develops an AE which requires anticoagulation therapy, the Investigator in consultation with the Medical Monitor will determine whether SD-101 injection should be continued or interrupted.

SD-101 should be permanently discontinued for any of the following:

- SD-101 dosing is delayed for more than 6 weeks
- DLT that occurs during the DLT assessment period in Phase 1 (Section 9.1)

- Clinically significant immune-related event
- Pembrolizumab is permanently discontinued

SD-101 will be permanently discontinued for any of the following adverse reactions (ARs):

- Severe or life-threatening ARs, including any of the following:
 - Any Grade 4 (life-threatening) AR
 - Grade 3 or 4 pneumonitis
 - Grade 4 diarrhea/colitis
 - Grade 4 hyperthyroidism
 - Grade 3 AST or ALT of $> 5 \times \text{ULN}$ or Grade 3 total serum bilirubin $> 3 \times \text{ULN}$
 - AST or ALT increases by greater than or equal to 50% relative to baseline and lasts for at least 1 week in patients with liver metastasis who begin treatment with a baseline Grade 2 AST or ALT of > 3 and $\leq 5 \times \text{ULN}$
 - Grade 3 or 4 nephritis
 - Any severe or Grade 3 AR that recurs
 - Inability to reduce corticosteroid dose (used for treatment of AEs) to 10 mg or less of prednisone or equivalent per day within 12 weeks of starting corticosteroids
- Observation of any other toxicities that in the opinion of the investigators suggests that there may be a significant increase in either the incidence or severity of any events seen with either single agent. In this case, the sponsor and investigators will review all safety data.

Pembrolizumab must be withheld for drug-related toxicities and severe or life-threatening AEs as listed in [Table 7-1](#). If a patient's AE prevents pembrolizumab dosing then SD-101 injection should be held if the AE also could at least be possibly related to SD-101. Delayed dosing of SD-101 would be preferred over completely skipping a dose as long as the interval between SD-101 dosing is not less than 5 days with subsequent return of SD-101 dosing to per protocol schedule of events. See [Section 7.7](#) for use of corticosteroids.

Grade 2 - 3 fatigue does not require the withholding of pembrolizumab or SD-101 treatment.

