9.2 Reasons for Stopping a Patient From Receiving Additional Treatment

NOTE: As of Amendment 9, the use of irRECIST for determination of disease progression is no longer applicable and this section has been revised accordingly. It is at the discretion of the investigator as per local standard of care and assessment guidelines whether to repeat imaging for confirmation and whether to continue a patient on study treatment until repeat imaging is obtained.

Patients will be discontinued from either trial treatment by the investigator for any of the following reasons:

- Noncompliance with trial procedures as determined by the investigator or sponsor
- Pregnancy in patient and/or initiation of breast feeding (see Section 10.3.7)
- Use of or need for prohibited medications (as described in Section 7.4)
- Confirmed PD per local standard of care and local assessment guidelines
- Intercurrent illness that prevents further administration of treatment
- Unacceptable AEs
- Adverse drug reaction that requires study drug discontinuation per protocol (see Section 7.6)

- Need for > 2 dose delays due to toxicity as per the dose modification guidelines described in Section 7.6
- If in the opinion of the investigator, a change or discontinuation of therapy would be in the best interest of the patient
- Patient has completed 35 doses and/or 2 years (Study Day 715) of pembrolizumab therapy

The investigator or designee must notify Dynavax when a patient has been discontinued from treatment. If SD-101 is discontinued prior to completion of planned study dosing, a patient may continue on pembrolizumab alone per investigator decision and approval of the Dynavax Medical Monitor.

In patients who have initial evidence of radiographic PD, it is at the discretion of the investigator whether to repeat imaging for confirmation and whether to continue a patient on study treatment until repeat imaging is obtained. This clinical judgment decision should be based on the patient's overall clinical condition, including ECOG PS, clinical symptoms, and laboratory data. Patients may receive pembrolizumab and SD-101 treatment while waiting for confirmation of PD if they are clinically stable as defined by the following criteria:

- Absence of signs and symptoms indicating disease progression
- No decline in ECOG PS
- Absence of rapid progression of disease
- Absence of progressive tumor at critical anatomical sites (eg, cord compression) requiring urgent alternative medical intervention

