11.4 Adverse Event Severity and Relationship to Trial Treatment

11.4.1 Severity Grading of Adverse Events

The severity of predefined AEs and other health changes will be assessed and confirmed by the investigator and will be graded using the NCI CTCAE Version 4.03 grading scale by system organ class ([National Cancer Institute 2010](#)). If the appropriate grading or description cannot be applied, then the investigator may elect to use the adapted NCI CTCAE, Version 4.03 ([Table 11-1](#)) to assess the AE.

Table 11-1: National Cancer Institute Common Terminology Criteria for Adverse Events (CTCAE, Version 4.03)

AE Severity	Definition
Grade 1	Mild; asymptomatic or mild symptoms; clinical or diagnostic observations only; intervention not indicated
Grade 2	Moderate; minimal, local or noninvasive intervention indicated; limiting age-appropriate instrumental ADL ^a
Grade 3	Severe or medically significant but not immediately life-threatening; hospitalization or prolongation of hospitalization indicated; disabling; limiting self-care ADL ^b
Grade 4	Life-threatening consequences; urgent intervention indicated
Grade 5	Death related to AE

Source: Adapted from NCI CTCAE, Version 4.03 ([National Cancer Institute 2010](#))

ADL = Activities of Daily Living; AE = adverse event; CTCAE = common terminology criteria for adverse events; NCI = National Cancer Institute.

^a Instrumental ADL refer to preparing meals, shopping for groceries or clothes, using the telephone, managing money, etc.

^b Self-care ADL refer to bathing, dressing and undressing, feeding self, using the toilet, taking medications, and not bedridden.

NOTE: For all AEs and SAEs, if there is a change in the severity after onset of either an AE or SAE, the AE or SAE should be reported as a single entry with the maximum severity grading captured.

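### Protocol 7.6 gives conflicting actions for SD-101 after a Grade 4 or a first Grade 3 drug-related reaction, and the delay limit in 9.2 does not match 7.6

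*Protocol*

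**What the plan says.** Protocol 7.6 withholds SD-101 for any Grade 3 or higher "injection-site reaction or drug-related AE that is not a DLT (see Section 9.1"), and adds that "SD-101 treatment may be resumed once the AE has resolved to Grade 0 or 1 with standard treatment". Later, the same section lists the adverse reactions (ARs) for which SD-101 is to be stopped permanently. The list opens with "Severe or life-threatening ARs, including any of the following". Its entries include "Any Grade 4 (life-threatening) AR", several named Grade 3 events (pneumonitis, AST/ALT, bilirubin, nephritis), and a severe or Grade 3 reaction on recurrence. Neither rule refers to the other.

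Table 11-1 (Protocol 11.4.1) describes Grade 3 as "Severe or medically significant but not immediately life-threatening". Appendix 5, used to grade injection-site reactions, also labels Grade 3 as severe.

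On delays, 7.6 prefers delaying an SD-101 dose to skipping it. In Phase 2 it ends SD-101 when 4 or more doses are missed because of AEs. It also ends SD-101 for a delay of more than 6 weeks, among other reasons. For pembrolizumab it allows two toxicity delays and stops the drug at a third occurrence. Protocol 9.2, whose list is introduced as reasons for stopping either of the two trial treatments, includes "Need for > 2 dose delays due to toxicity as per the dose modification guidelines described in Section 7.6".

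This text is in force. The Amendment 9 note in 4.1.2 keeps enrolled Phase 2 patients on treatment per protocol, and 7.6 was revised at that amendment, not withdrawn.

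**The concern.** Whether a patient may receive SD-101 again after a severe related event should not depend on which sentence the site reads. As written, two sites could treat the same Grade 4 event differently and each cite 7.6. That is first a patient-safety matter. It also touches the analysis: SAP 9.7.3 tabulates TEAEs leading to study drug discontinuation, and that table would partly reflect how each site read the rule as well as the toxicity itself. The delay provisions raise the same problem on a smaller scale.

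**Working it through.** This is mainly a comparison of text; only the last step uses arithmetic.

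**Does the DLT exception separate the two rules?** Protocol 9.1 defines DLTs for dose escalation, from Day 1 through Day 29, and the stop provisions in 7.6 tie them to Phase 1. Inside that window most Grade 4 events were DLTs (hematologic, and non-hematologic other than laboratory), so they fell outside the hold rule. In Phase 2 the exception has nothing to act on.

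**The provisions side by side, for Phase 2:**

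| Event | One provision | Another provision |
|---|---|---|
| Grade 4 related event | 7.6 hold rule: Grade 3 or higher, may resume at Grade 0 or 1 | 7.6 stop list: "Any Grade 4 (life-threatening) AR", permanent stop |
| First Grade 3 reaction, not a named event | 7.6 stop-list heading: severe reactions, permanent stop | 7.6 recurrence bullet and hold rule: imply hold and resume the first time |
| Third toxicity delay of SD-101, each under 6 weeks, no dose missed | 9.2: more than 2 delays, stop | 7.6: 0 missed doses against a limit of 4, no delay over 6 weeks, so neither SD-101 limit is reached |

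**Grade 4.** The hold rule starts at Grade 3 and has no ceiling. Protocol 9.3.1 follows the same pattern for local reactions: delay or skip until Grade 0 or 1, again with no upper grade. No text says the stop list takes precedence.

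**First Grade 3.** The heading uses the word that both grading tables attach to Grade 3, and it introduces its entries as examples, so the list is not closed. On that wording a first Grade 3 reaction is covered. But a bullet that acts only on recurrence has a purpose only if the first occurrence does not already end treatment.

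**Delays.** Section 9.2 counts delays, while the SD-101 limits in 7.6 count missed doses or the length of a delay. The only count of delays in 7.6 is the pembrolizumab one, and it agrees with 9.2: two allowed, stop at the third. The mismatch therefore arises only if the 9.2 bullet is applied to SD-101, which the opening words of its list permit.

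**How often severe related events occur.** Protocol 2.6 reports that Grade 3 or higher "treatment-related AEs were observed in 59.1% patients". The denominator 22 is printed in the same item for immune-related AEs. Then 13/22 = 0.5909, or 59.1%, as stated. The companion figures agree: 3/22 = 13.6% (myalgia; injection-site pain) and 2/22 = 9.1% (printed as 9%). Among denominators from 15 to 30, only 22 fits all three. The exact 95% interval for 13/22 is 36.4% to 79.3%.

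**The case against.** The strongest reply is that ordinary reading resolves most of this. The resume sentence is permissive and the stop list is mandatory and more specific, so a site can comply with both by holding SD-101 after a Grade 4 event and not resuming. Section 9.2 also lists adverse drug reactions that require discontinuation under 7.6, which supports treating the stop list as operative. For Grade 3, taking the heading to cover every such event would make the named Grade 3 bullets and the recurrence bullet redundant. Table 11-1 is a fallback scale, and the recurrence bullet sets severe and Grade 3 side by side as if they differed. The 9.2 delay bullet probably restates the pembrolizumab limit: the same list has another single-drug item (35 doses or 2 years of pembrolizumab), and stopping pembrolizumab stops SD-101 anyway.

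These are plausible accounts of the intent, and the one for 9.2 is likely. None is written down. The documents state no precedence, the hold rule has no cross-reference, and the 9.2 bullet names no drug. Protocol 11.2.4 may make an adverse reaction narrower than a drug-related AE, but the protocol does not use that distinction to separate the two rules. The Amendment 9 note in 9.0 leaves discontinuation decisions to local standard of care, yet the note in 8.2 still directs investigators to the stopping rules in 9.2, so it settles nothing.

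A reader might add fatigue as a further conflict, because 7.6 says that Grade 2 to 3 "fatigue does not require the withholding of pembrolizumab or SD-101 treatment". That does not hold. It is a named exception to a general rule in the same section, and at most deserves a cross-reference.

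**Conclusion.** The concern stands in three parts of unequal strength. The Grade 4 conflict is the firmest: in Phase 2 the same event may be resumed under one sentence and must end SD-101 under another. The first Grade 3 case is a conflict on the wording, though a reconciling reading exists. The 9.2 delay bullet is a mismatch that naming the drug would probably cure. Together they warrant correction because dosing continues under this text.

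The size is unknown. A reader might infer that 59% of patients met conflicting rules. The documents do not support that: the 59.1% counts patients with any Grade 3 or higher event related to either drug, and Protocol 2.6 gives no counts of Grade 4 or recurrent Grade 3 events and reports no DLTs. It is an upper bound on how often the severe-event rules came into play in those data, assuming that Grade 3 or higher injection-site reactions are counted in it. It says nothing about delays. That the data are from Phase 1 is itself inferred, from the denominator, the 1.0 to 8.0 mg range and the DLT statement.

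Two other inferences should be avoided. Section 7.6 does not make 4 missed doses the only ground for stopping SD-101; it also lists a delay over 6 weeks, permanent discontinuation of pembrolizumab, clinically significant immune-related events and the listed reactions. And nothing in the documents shows that sites have in fact acted differently.

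**What to change.** The sponsor should reconcile the hold rule, the permanent-stop list and the pembrolizumab delay limit in 7.6 with the delay bullet in 9.2. The revised text should:

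- state which provision governs a Grade 4 adverse reaction;
- state which provision governs a first Grade 3 adverse reaction, and align the stop-list heading with its bullets;
- add a cross-reference from the hold rule to the stop list (and, if wanted, to the fatigue exception);
- name the drug or drugs to which the 9.2 delay limit applies.

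A single SD-101 action table by grade and event type, cited from 9.2, would do this. Which rule is clinically right is for the sponsor's clinicians, and no view is offered here.

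The cost is a clarification letter or a short amendment, with no new data or procedures.

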7.5 Permitted Therapy

Topical or inhaled or intranasal corticosteroids (with minimal systemic absorption) and non-absorbed intra-articular steroid injections are permitted to treat AEs and may be continued with permission of the Dynavax Medical Monitor. Systemic corticosteroids required for the control of infusion reactions or immune-related AEs must be tapered and be at non-immunosuppressive doses (≤ 10 mg per day of prednisone or equivalent) before the next administration of SD-101 or pembrolizumab. A brief (< 24 hours) course of steroids for prophylaxis against contrast dye allergy is permitted for patients undergoing tumor assessments per institutional standard. Guidelines for steroid use to treat immunologic AEs are listed in Section 7.7.

Acetaminophen (maximum 3 g per day), ibuprofen, and/or ondansetron may be used post-SD-101 treatment to treat flu-like symptoms and pre-dose as prophylaxis. Pre- and post-SD-101 treatment prophylaxis with these agents is allowed but not encouraged for the first SD-101 dose for a patient in Phase 1 unless recommended per the Dynavax Medical Monitor. The sponsor may make further recommendations with regards to prophylaxis treatments for potential flu-like symptoms as the study is ongoing. See Section 9.3 for additional details.

Efforts should be made to keep all other concurrent medications at stable doses during the trial and to refrain from starting any new medications, unless clinically indicated. Therapy to prevent or treat local and/or systemic reactions following administration of either trial drug may include analgesics, antipyretics, and antihistamines.

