Corticosteroid taper should be initiated upon AE improving to Grade 1 or less and continue to taper over at least 4 weeks.

For situations where pembrolizumab has been withheld, pembrolizumab can be resumed after AE has been reduced to Grade 1 or 0 and corticosteroid has been tapered. Pembrolizumab should be permanently discontinued if AE does not resolve within 12 weeks of last dose or corticosteroids cannot be reduced to ≤ 10 mg prednisone or equivalent per day within 12 weeks.

For severe and life-threatening irAEs, IV corticosteroid should be initiated first followed by oral steroid. Other immunosuppressive treatment should be initiated if irAEs cannot be controlled by corticosteroids.

Immune-related AEs	Toxicity grade or conditions (CTCAE v4.0)	Action taken to pembrolizumab	irAE management with corticosteroid and/or other therapies	Monitor and follow-up
Pneumonitis	Grade 2	Withhold	Administer corticosteroids (initial dose of 1-2 mg/kg prednisone or equivalent) followed by taper	Monitor participants for signs and symptoms of pneumonitis Evaluate participants with suspected pneumonitis with radiographic imaging and initiate corticosteroid treatment Add prophylactic antibiotics for opportunistic infections
	Grade 3 or 4, or recurrent Grade 2	Permanently discontinue		

Table 7-1: Dose Modification and Toxicity Management Guidelines for Immune-related Adverse Events Associated with Pembrolizumab (Cont'd)

Immune-related AEs	Toxicity grade or conditions (CTCAEv4.0)	Action taken to pembrolizumab	irAE management with corticosteroid and/or other therapies	Monitor and follow-up
Diarrhea / Colitis	Grade 2 or 3	Withhold	Administer corticosteroids (initial dose of 1-2 mg/kg prednisone or equivalent) followed by taper	Monitor participants for signs and symptoms of enterocolitis (ie, diarrhea, abdominal pain, blood or mucus in stool with or without fever) and of bowel perforation (ie, peritoneal signs and ileus). Participants with \geq Grade 2 diarrhea suspecting colitis should consider GI consultation and performing endoscopy to rule out colitis. Participants with diarrhea/colitis should be advised to drink liberal quantities of clear fluids. If sufficient oral fluid intake is not feasible, fluid and electrolytes should be substituted via IV infusion.
	Grade 4	Permanently discontinue		

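### Protocol Sections 7.2, 7.5, 7.6, 9.2 and Table 7-1 do not give one consistent condition for resuming SD-101 after a corticosteroid hold

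*Protocol*

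**What the plan says.** Five places in the protocol bear on the same decision.

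- **Section 7.5** covers "Systemic corticosteroids required for the control of infusion reactions or immune-related AEs". The condition it sets is that they "must be tapered and be at non-immunosuppressive doses (≤ 10 mg per day of prednisone or equivalent) before the next administration of SD-101"; the same condition applies to pembrolizumab. Stopping the steroid is not required.
- **Section 7.6, hold:** "SD-101 should be withheld if a patient requires greater than 10 mg per day of prednisone or equivalent to treat an AE".
- **Section 7.6, resumption:** "SD-101 may be resumed when the corticosteroid is discontinued and pembrolizumab is resumed".
- **Section 7.6, permanent stop:** the listed reasons include "Inability to reduce corticosteroid dose (used for treatment of AEs) to 10 mg or less of prednisone or equivalent per day within 12 weeks", counted from the first steroid dose, and, separately, "SD-101 dosing is delayed for more than 6 weeks".
- **Table 7-1 (Section 7.7):** "pembrolizumab can be resumed after AE has been reduced to Grade 1 or 0 and corticosteroid has been tapered". The taper begins when the event improves to Grade 1 or less and runs for at least 4 weeks.
- **Sections 7.2 and 9.2:** after a temporary hold of pembrolizumab, SD-101 and pembrolizumab restart on the same day.

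Neither Section 7.5 nor Section 7.6 refers to the other's steroid condition, and no order of precedence is given. Both remain in force. Amendment 9 closed enrolment but continued assigned dosing in Phase 2, and it revised Section 7.6 for another reason while keeping the resumption sentence.

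**The concern.** Section 7.5 sets a dose ceiling, while the resumption sentence in Section 7.6 sets complete discontinuation. Section 7.6 is also uneven within itself: the hold and the steroid-based permanent stop both turn on 10 mg/day, but resumption turns on zero. The same-day rule and Table 7-1 then tie SD-101 to the return of pembrolizumab, which does not clearly wait for zero.

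At stake is a re-treatment rule after toxicity. If sites read it differently, similar patients could have different SD-101 exposure, and some could lose SD-101 permanently because of the reading chosen rather than their condition.

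**Working it through.** The plan states no figure to reproduce. The check is a comparison of the rules plus two short calculations.

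**1. Who can be in the gap.** The Section 7.6 resumption sentence follows a hold triggered above 10 mg/day. A patient must therefore have exceeded 10 mg/day to treat an adverse event and then come down to a dose above 0 and up to 10 mg/day.

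**2. Do Table 7-1 steroid courses trigger the hold?** The lowest weight-based starting dose in Table 7-1 is 0.5 mg/kg (Grade 2 liver enzyme or bilirubin elevation). Taking this as a daily dose (assumption), it exceeds 10 mg/day for any body weight above 10 / 0.5 = 20 kg. In practice, every adult started on a weight-based Table 7-1 course meets the hold criterion.

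**3. Worked case.** A patient has a Grade 2 immune-related event, not judged clinically significant. Pembrolizumab is withheld, and SD-101 is withheld for a steroid dose above 10 mg/day. The event is now Grade 1, prednisone is down to 5 mg/day, and the site resumes pembrolizumab.

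| Rule | Position at 5 mg/day |
|---|---|
| Section 7.5 | met for both drugs |
| Table 7-1 | pembrolizumab may return, if a taper to 5 mg/day counts as tapered |
| Sections 7.2 and 9.2 | SD-101 restarts that day |
| Section 7.6 | SD-101 may not restart, because the steroid has not been stopped |

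Giving SD-101 departs from Section 7.6. Holding it departs from Sections 7.2 and 9.2.

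**4. Can the choice decide a permanent stop?** The limit on SD-101 delay is 6 weeks and the minimum taper is 4 weeks. Section 7.6 does not say when the delay starts to count. If it counts from a dose missed at event onset (assumption), then 6 − 4 = 2 weeks is the most that can pass before the taper starts, if the steroid is to be stopped before the limit is exceeded. A longer taper, or slower improvement to Grade 1, uses up that margin. Under the ceiling in Section 7.5, the threshold is reached earlier in the same taper.

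**5. Missed-dose rule.** Section 7.6 also stops SD-101 permanently in Phase 2 at four or more doses missed for adverse events. In the three-weekly part of the schedule, the fourth consecutive miss comes 3 × 3 = 9 weeks after the first, so the 6-week limit applies first. The delay limit is the more direct consequence there.

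**The case against.** The strongest answer is that Section 7.5 states a necessary condition, not permission. On that reading it is a floor for both drugs, Section 7.6 adds a stricter condition for SD-101, and a site that waits for full discontinuation breaches neither. This is fair for those two sections alone. The same-day rule is what breaks it once pembrolizumab has been resumed during the taper.

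A site could still satisfy every sentence by keeping both drugs on hold until the steroid is stopped, since the wording on resuming pembrolizumab is permissive. Table 7-1 could also be read as meaning a completed taper. Nothing in the protocol directs either course, and either would leave the 10 mg/day ceiling in Section 7.5 with little work to do for these patients.

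The second objection concerns reach, and much of it stands. Section 7.6 ends SD-101 permanently for an immune-related event judged clinically significant and for listed Grade 3 or 4 reactions. The hold sentence cross-refers to infusion reactions, yet Table 9-1 lists corticosteroids only for Grades 3 and 4, where no further dosing is allowed. The group is not empty, though: Table 7-1 withholds rather than stops pembrolizumab for several steroid-treated events, and clinical significance is not defined.

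Three stronger readings are tempting, and the documents do not support them:

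- A reader might infer that every patient on a low steroid dose is affected. A patient who never exceeded 10 mg/day was not held under this rule, so there is nothing to resume.
- A reader might infer that sites will diverge. The text shows only that they could.
- A reader might infer damage to the response results. Phase 2 efficacy data are no longer collected under Amendment 9, and the documents show no such effect.

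**Conclusion.** The inconsistency is real and narrow. It applies when SD-101 was held for more than 10 mg/day, the steroid has come down to a dose above 0 and up to 10 mg/day, and pembrolizumab is resumed at that dose. The rules then cannot all be followed.

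The number of such patients is not given. Phase 1 is complete, and SD-101 dosing in Phase 2 ends by Day 358, 400 or 421 depending on the cohort. The documents do not say how many patients were still receiving it, so the practical reach is unknown and could be nil. The link to permanent discontinuation rests on the assumption about when the 6-week delay starts to count.

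This is an inconsistency between passages, of low priority statistically. It is worth correcting because it governs re-treatment after toxicity.

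**What to change.** Reconcile Sections 7.2, 7.5, 7.6, 9.2 and Table 7-1 so that the protocol states one consistent condition for resuming SD-101 after a corticosteroid hold, with cross-references between the sections. The reconciled text should make clear how that condition fits with the same-day restart of the two drugs and with the 6-week limit. Which condition applies is for the sponsor to decide; this review proposes none.

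The cost is a short clarification or amendment and a notice to sites with patients still on SD-101. Sample size and planned analyses do not change.
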